4.1 Inclusion Criteria

1. Histologically confirmed diagnosis of gastric and GEJ adenocarcinoma
2. Measurable or non-measurable disease by Response Evaluation Criteria in Solid Tumors (RECIST) 1.1. Stage IV or recurrent disease is required. An irradiated lesion is considered evaluable only if it has shown enlargement since the completion of last radiation.
3. Patients must have received and progressed with prior therapy. Prior therapy with ramucirumab is not allowed. Patients must have recovered from the toxic effects of the previous anti-cancer chemotherapy (with the exception of alopecia).
4. ECOG Performance Score 0 or 1
5. Estimated life expectancy > 3 months
6. Adequate bone marrow, liver and renal function as assessed by the following:
 - o Hemoglobin > 8.0 g/dl
 - o Absolute neutrophil count (ANC) > 1,000/mm³ independent of growth factor support
 - o Platelet count > 100,000/mm³
 - o Total bilirubin < 1.5 times ULN unless bilirubin rise is due to Gilbert's syndrome or of non-hepatic origin
 - o AST, ALT and Alkaline Phosphatase \leq 2.5 times the ULN (\leq 5 x ULN for patients with liver involvement)
 - o Creatinine clearance \geq 30 ml/min
7. Patients must not have had chemotherapy, major surgery, monoclonal antibody therapy or experimental therapy within the 28 days prior to the start of TAS 102 administration.
8. Women of childbearing potential must have a negative serum pregnancy test performed within 7 days prior to the start of study drug. Post-menopausal women (defined as no menses for at least 1 year) and surgically sterilized women are not required to undergo a pregnancy test.
9. Subjects (men and women) of childbearing potential must agree to use adequate contraception beginning at the signing of the ICF until at least 4 months for both females and males after the last dose of study drug. The definition of adequate contraception will be based on the judgment of the principal investigator or a designated associate.
10. Subjects must be able to understand and be willing to sign the written informed consent form. A signed informed consent form must be appropriately obtained prior to the conduct of any trial-specific procedure. Subjects must be willing and able to comply with scheduled visits, treatment schedule, laboratory testing, and other study requirements.

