5.1.1 Management (dose Modifications and dose delays) for Treatment-Related Toxicity

All toxicities will be graded according to National Cancer Institute's (NCI's) Common Terminology Criteria for Adverse Events (CTCAE) (NCI CTCAE v 5). The study investigator will determine if either or both medications should be held.

Dose reductions for AEs related to TAS 102 are permitted dose reductions to a minimum dose of 20mg/m² twice a day in 5mg/m² steps. After dose reduction, escalation of dose is not allowed.

Table 1. TAS 102 dose modifications

TAS 102 dose (BID)	BSA (m ²)*	Dosage in mg (BID)	Total daily dose (mg)	Tablets per dose	
				15mg	20mg
Starting dose					
35mg/m ²	<1.07	35	70	1	1
	1.07-1.22	40	80	0	2
	1.23-1.37	45	90	3	0
	1.38-1.52	50	100	2	1
	1.53-1.68	55	110	1	2
	1.69-1.83	60	120	0	3
	1.84-1.98	65	130	3	1
	1.99-2.14	70	140	2	2
	2.15-2.29	75	150	1	3
	≥ 2.30	80	160	0	4
Level 1 dose reduction: from 35mg/m ² to 30mg/m ²					
30mg/m ²	<1.09	30	60	2	0
	1.09-1.24	35	70	1	1
	1.25-1.39	40	80	0	2
	1.4-1.54	45	90	3	0
	1.55-1.69	50	100	2	1

	1.70-1.94	55	110	1	2
	1.95-2.09	60	120	0	3
	2.10-2.28	65	130	3	1
	≥ 2.29	70	140	2	2
Level 2 dose reduction: from 30mg/m ² to 25mg/m ²					
25mg/m ²	<1.10	25	50	2 (PM)¶	1 (AM)¶
	1.10-1.29	30	60	2	0
	1.30-1.49	35	70	1	1
	1.50-1.69	40	80	0	2
	1.70-1.89	45	90	3	0
	1.90-2.09	50	100	2	1
	2.09-2.29	55	110	1	2
	≥ 2.30	60	120	0	3
Level 3 dose reduction: from 25mg/m ² to 20mg/m ²					
20mg/m ²	<1.14	20	40	0	1
	1.14-1.34	25	50	2 (PM)¶	1 (AM)¶
	1.35-1.59	30	60	2	0
	1.60-1.94	35	70	1	1
	1.95-2.09	40	80	0	2
	2.10-2.29	45	90	3	0
	≥ 2.29	50	100	2	1

* Calculate BSA to 2 decimal places.

¶ At a total daily dose of 50mg, patients should take 1 x 20mg tablet in the morning and 2 x 15mg tablets in the evening.

Dose reductions of ramucirumab will be allowed only for proteinuria with 6 mg/kg for first episode of proteinuria (> 2 g/24 hours) and with 5 mg/kg for second episode of proteinuria (> 2 g/24 hours). Only dose delay will be allowed for the other AEs related to ramucirumab.

Table 2. Ramucirumab dose modifications

Starting dose	8mg/kg
Level 1 dose reduction	6mg/kg
Level 2 dose reduction	5mg/kg

Dose modifications will not be required for AEs that are clearly not attributed to TAS 102 or ramucirumab (such as an accident) or for laboratory abnormalities that are not deemed to be clinically significant.

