Neutrophils	<500/mm ³	<0.5x10 ⁹ /L	≥1500/mm ³ (IU: ≥1.5x10 ⁹ /L)	Details below¶
Platelets	<50,000/mm ³	<50x10 ⁹ /L	≥75,000/mm ³ (IU: ≥75x10 ⁹ /L)	Details below¶

* These resumption criteria apply to the start of the next cycle for all patients regardless of whether or not the hold criteria were met. Both conventional and SI (International System) units are presented in CTCAE v. 5.

¶ 1) ≤ Grade 3 neutropenia or thrombocytopenia

- If there are no complications (such as fever, infection or hemorrhage), there is no need to reduce the dose of TAS 102
- If there are complications, the necessity of reducing dose should be considered also with regard to safety.
- For neutropenia, pegfilgrastim or filgrastim can be administered at investigator's discretion.

2) Grade 4 neutropenia or thrombocytopenia

- When there are no complications, but initiation of the next cycle is delayed by more than one week, dose should be reduced by 1 level (Table 1) when starting next cycle (dose is not reduced when administered on the same weekday). If initiation is not delayed by more than one week, the next cycle can be initiated at the same dose level.
- If there are complications, in consideration of the safety of the patient, dose should be reduced by 1 level (Table 1) when starting the next cycle.
- For neutropenia, pegfilgrastim or filgrastim can be administered at investigator's discretion.

5.1.1.1.3 Dose resumption timing of TAS 102

If the patient recovers from the toxicities to the resumption criteria defined above during the 2-week treatment period (treatment Days 1 through 5, 8 through 12), and no dose reduction is required, study drug therapy may be resumed during that cycle.

If a dose reduction is required, study drug therapy should be resumed at the start of the next cycle at the appropriate dose level according to instructions provided in Table 1 and 2. If the study drug dose is reduced, it must not be increased for subsequent cycles.

If the toxicities that are defined above recover during the recovery period (Days 13 through 28), start the next cycle on schedule at the appropriate dose level according to instructions provided in Table 1, 3 and 4.

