6.8 Calendar

	Screening within 28 days of C1D1 ^m	Cycle 1 Day 1 ± 3 days and subsequent cycles	Cycle 1 day 15 ± 3 days	Cycle X day 1 ± 5 day	Cycle X day 15 ± 5 day	End of treatment visit ⁿ	Safety follow-up	Survival follow-up
Complete History/Physical^a	X							
History & Assessment^b		X	X	X		X	X	
Toxicity Notation		X	X	X		X	X	
ECOG	X	X	X	X		X		
ECG	X							
Tumor Measurement/ Disease Assessment^c	X			X		X		
Hematology^d	X	X	X	X	X	X		
Chemistry^e	X	X	X	X	X	X		
Coagulation^f	X							
Urinalysis^g	X	X		X		X		
24hr urine protein^h			X	X	X	X		
Hepatitis and HIV Screeningⁱ	X							
Serum	X							

Pregnancy, if applicable j								
Survival f/u k								X
Diary – Issued/Retur- ned¹		X		X				

- a. *Complete medical history and physical examination* including demographics, surgery, therapies, medications, smoking, alcohol history, co-existing diseases, allergy, NYHA classification, vital signs (heart rate, respiration rate, temperature and BP), height, weight and review of systems.
- b. *History and assessment* including brief examination, vital signs and review of systems. Note all toxicities and adverse events, using CTCAE version 5.
- c. Tumor assessment using CT or MRI (at investigator's discretion) will be collected at screening, after every 3 cycles, and as clinically indicated. Tumor response will be assessed using RECIST 1.1 criteria. Tumor measurement/disease assessment should be performed within 7 days at the beginning of every 3rd cycle.
- d. Hemoglobin, hematocrit, red blood cell count, white blood cell count with differential (neutrophils, bands, lymphocytes, monocytes, eosinophils and basophils) and platelet count.
- e. ALT, AST, alkaline phosphatase, total bilirubin, direct bilirubin, LDH, creatine kinase, lipase, amylase glucose, calcium, phosphate, magnesium, bicarbonate, sodium, potassium, chloride, creatinine, blood urea nitrogen (BUN), total protein and albumin.
- f. PT-INR and aPTT.
- g. Urinalysis including blood, glucose, protein, specific gravity. If dipstick or routine urinalysis indicates proteinuria $\geq 2+$, a 24-hour urine collection must be obtained in 2 weeks.
- h. If necessary
- i. Hepatitis B surface antigen, surface antibody, core antigen and Hepatitis C antibody
- j. Pregnancy test will be performed at baseline for WOCBP and then only as clinically indicated

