8.1 Adverse Events

8.1.1 Definitions

A serious adverse event is an undesirable sign, symptom or medical condition which:

1. Is fatal or life-threatening.
2. Requires or prolongs hospitalization.
3. Results in persistent or significant disability/incapacity.
4. Constitutes a congenital anomaly or a birth defect.
5. Is medically significant, may jeopardize the subject and may require medical or surgical

intervention to prevent one of the outcomes listed above.

Information about all adverse events, whether volunteered by the subject, discovered by investigator questioning, or detected through physical examination, laboratory test or other means, will be collected and recorded and followed as appropriate. An adverse event is any undesirable sign, symptom or medical condition occurring after starting study treatment.

Medical conditions/diseases present before starting study treatment are only considered adverse events if they worsen after starting study treatment. Abnormal laboratory values or test results constitute adverse events only if they induce clinical signs or symptoms or require therapy.

Full information from serious adverse events as well as adverse events concerning medication errors and overdose will be reported to Taiho Drug Safety or Designee. **This can be performed by faxing it to Taiho or designee at [contact] or via e-mail at [contact] (please note the underscore between '102' and 'Safety').**

In addition to the above, fatal events will also be documented by a separate death form, instead of reporting them as AE CTCAE grade.

Events not considered to be serious adverse events are hospitalizations for the:

- Routine treatment or monitoring of the studied indication, not associated with any deterioration in condition.
- Treatment, which was elective or pre-planned, for a pre-existing condition that did not worsen.
- Treatment on an emergency, outpatient basis for an event not fulfilling any of the definitions of serious given above and not resulting in hospital admission.

Pregnancy, although not itself a serious adverse event, should also be reported on a serious adverse event form or pregnancy form and be followed up to determine outcome, including spontaneous or voluntary termination, details of birth, and the presence or absence of any birth defects or congenital abnormalities.

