9.3 Statistical analysis

Overall survival (OS) is defined as the time from starting on trial to date of death due to any cause and progression-free survival (PFS) is defined as the duration of time from start of treatment to time of progression or death, whichever comes first. The final analysis will be conducted after the follow-time of the last patient exceeds 6 months. The primary endpoint of the study is OS at 6 month. The experimental treatment will be deemed to have good activity if ≥ 15 out of 25 evaluable patients survive 6 months or more. OS will be estimated using the Kaplan-Meier method and the two-sided 95% confidence interval (CI) for median OS will be computed using log-log transformation.

The secondary endpoints in this study include toxicity, PFS and the objective response rate (ORR) defined as (complete response (CR) + partial response (PR)) using RECIST 1.1 criteria (Appendix A). ORR will be reported with 95% CI computed by the Clopper-Pearson method. The frequency and severity of adverse events and tolerability of the regimen will be summarized using descriptive statistics. PFS with 95% CI will be estimated. As exploratory objective, the association between biomarkers and clinical outcomes (ORR, OS and PFS) will be examined using multiple logistic regression and the multivariable Cox regression model. A p-value of <0.05 will be considered statistically significant. Frequency and severity of adverse events will be summarized using descriptive statistics.

10. Data Recording

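### Patients may enter with an ANC just above 1,000/mm³, but every later TAS 102 cycle requires at least 1,500/mm³, with no exception for a low baseline

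*Combined protocol and SAP*

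**What the plan says.** **Entry.** Section 4.1 item 6 and the synopsis require "Absolute neutrophil count (ANC) > 1,000/mm³ independent of growth factor support". Item 3 adds "Patients must have recovered from the toxic effects of the previous anti-cancer chemotherapy", with alopecia the only exception and no neutrophil value given. Item 7 imposes a 28-day washout. Section 6.2 schedules hematology on Cycle 1 Day 1, or accepts a screening sample taken within 5 days of it, but states no count that must be met there.

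**Later cycles.** Table 4 (section 5.1.1.1.2) holds TAS 102 when neutrophils are below 500/mm³ and allows resumption at 1,500/mm³ or more. Its footnote says: "These resumption criteria apply to the start of the next cycle for all patients regardless of whether or not the hold criteria were met". Section 5.1.1.1.3 lets the next cycle slip by at most 28 days, after which study medication stops. After uncomplicated grade 4 neutropenia, a delay of more than one week brings a one-level dose reduction, and a reduced dose may not be raised again.

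**Flexibility.** Section 5.1.1 says "The study investigator will determine if either or both medications should be held", and does not require dose modification for events clearly not attributed to the study drugs "or for laboratory abnormalities that are not deemed to be clinically significant". Table 4's notes and section 5.2 leave G-CSF to the investigator. The section 6.8 calendar gives the visit window as "Cycle X day 1 ± 5 day".

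**The concern.** The same count is high enough for a full first cycle and too low to begin any later one. For a patient in the gap, complete marrow recovery to baseline does not satisfy the restart rule: the count has to end up above where it began.

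What is at stake is the delivery of TAS 102 and the reading of tolerability, a secondary objective. A delay, or G-CSF given only to lift a patient above baseline, would reflect the entry rule rather than toxicity of the combination. Section 9.3 would not separate the two. It says "The frequency and severity of adverse events and tolerability of the regimen will be summarized using descriptive statistics" and names no summary of cycle delay or dose intensity. Under section 8.1.1, "Abnormal laboratory values or test results constitute adverse events only if they induce clinical signs or symptoms or require therapy", so treating a low baseline count with G-CSF could arguably turn it into a recorded event. The same section counts pre-existing conditions only if they worsen. Misattribution is therefore possible, but not certain.

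**Working it through.** The plan gives no figure on this point to reproduce. The check compares two written thresholds.

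**Inputs**
- Entry: ANC above 1,000/mm³ (section 4.1 item 6; synopsis).
- Start of next cycle: ANC 1,500/mm³ or more, all patients (Table 4 and footnote).
- Within-cycle hold: ANC below 500/mm³ (Table 4).
- Platelets, for comparison: entry above 100,000/mm³ (item 6), resumption at 75,000/mm³ or more (Table 4).

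**Step 1: apply both rules to the same count.** The rise needed is 1,500 / entry ANC − 1.

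| ANC (/mm³) | Eligible? | May start next cycle? | Rise above baseline needed |
|---|---|---|---|
| 1,000 | no | no | not applicable |
| 1,001 | yes | no | 1,500/1,001 − 1 = 49.9% |
| 1,250 | yes | no | 1,500/1,250 − 1 = 20.0% |
| 1,499 | yes | no | 1,500/1,499 − 1 = 0.07% |
| 1,500 | yes | yes | none |

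The affected band lies between 1,000 and 1,500/mm³. The rise required depends on where in it the patient enters, from almost nothing to one half.

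**Step 2: is this a general pattern?** No. Any platelet count that permits entry already exceeds the restart level, since 100,000 is above 75,000. Of the two counts in Table 4, only the neutrophil rule is inverted.

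**Step 3: does other text exempt these patients?**
- The section 5.1.1 sentence on holding concerns which drug is held. It does not mention the cycle-start level.
- The relief for clinically insignificant laboratory values is worded for dose modifications, while the section heading lists modifications and delays separately. It may soften the rule but does not clearly waive a specific footnote covering all patients.
- Section 10.3 requires conduct exactly as the protocol describes, emergencies apart, so starting Cycle 2 at 1,200/mm³ could be recorded as a deviation.
- G-CSF can lift the count, but is discretionary.
- The 5-day window absorbs only a short wait.

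No sentence in sections 4, 5.1.1, 5.2 or 6 allows a restart at baseline.

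**Step 4: what follows if the level is not met?** First, delay or G-CSF. A permanent dose reduction on the no-complication route needs grade 4 neutropenia and a delay of more than one week. Discontinuation needs a delay of more than 28 days, which supposes that G-CSF was not used or did not work.

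**Step 5: does this reach the design?** No. The Simon rule in section 9.2 (7 of 15, then 15 of 25; 45% against 70%) contains no neutrophil term, and overall survival at 6 months is defined without reference to dosing.

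**The case against.** The strongest reply is that the two floors answer different questions and can both be followed. The entry floor describes an unsupported marrow after a washout and recovery from earlier toxicity. The restart floor asks whether the marrow has recovered from a cytotoxic cycle just given. A stricter restart test is defensible, and nothing in the documents requires the two levels to match. Item 3 may also be read to exclude counts still depressed by earlier chemotherapy, and G-CSF means that a delay is not forced.

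Most of this stands as a limit on size. It does not remove the gap. Item 3 gives no neutrophil value, so a patient at 1,200/mm³ can be judged recovered. A restart test meant to detect recovery from the last cycle also fails in that purpose when full recovery to an eligible baseline does not pass it.

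The documents do not support three stronger readings that a reader might infer:
- *That the protocol regards 1,001 to 1,499/mm³ as unsafe for dosing.* Within a cycle Table 4 holds TAS 102 only below 500/mm³, and uncomplicated neutropenia of grade 3 or lower needs no dose reduction. The higher level governs cycle starts only.
- *That the entry floor costs a known share of dose intensity.* Any delay of d days reduces dose intensity over that interval to 28/(28 + d), whatever caused it. Patients entering at or above 1,500/mm³ can be delayed too, and nothing in the documents gives the extra delay due to the entry floor.
- *That affected patients always need a large rise.* Near the top of the band the rise is negligible.

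**Conclusion.** The mismatch is in the current text and no written exception closes it. A patient who enters in the gap and returns exactly to baseline cannot begin Cycle 2 of TAS 102 on schedule unless G-CSF raises the count. Confidence in that reading is high.

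The effect is minor. How many of the 25 patients would fall in the gap cannot be computed; that the number is small is a judgement resting on the recovery and washout requirements. The expected consequence per affected patient is a delayed cycle or G-CSF use. Permanent reduction or discontinuation requires further, unlikely events. The conclusion assumes that the footnote is applied as written; an investigator who relied on the general discretion in section 5.1.1 might start the cycle anyway, but the text leaves that unclear.

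**What to change.** In section 4.1 item 6 and the synopsis, change the neutrophil criterion to ANC 1,500/mm³ or more, independent of growth factor support. State that it must be met on the Cycle 1 Day 1 hematology, or on the screening sample that section 6.2 accepts within 5 days. Leave the Table 4 restart level and the one-week and 28-day limits as they are.

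An alternative is a sentence in the Table 4 footnote allowing restart at baseline for patients who enter below 1,500/mm³. It would avoid screen failures, but would still allow a full-dose first cycle below the protocol's own cycle-start level and would relax the restart rule for patients who begin with the lowest counts. Raising the entry level is the cleaner choice.

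The cost is a short amendment in two places and a few more screen failures in a 25-patient, single-institution trial. No new tests and no change to the sample size are needed.

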4.2 Exclusion Criteria

1. Subjects with active CNS metastases are excluded. If CNS metastases are treated and subjects are at neurologic baseline for at least 2 weeks prior to enrollment, they will be eligible but will need a Brain MRI prior to enrollment.
2. Women who are pregnant or breast-feeding
3. Prior therapy with ramucirumab, bevacizumab, regorafenib or TAS 102.
4. Previous or concurrent cancer within 3 years prior to treatment start EXCEPT for curatively treated cervical cancer in situ, non-melanoma skin cancer, superficial bladder tumors [Ta (non-invasive tumor), Tis (carcinoma in situ) and T1 (tumor invades lamina propria)].
5. Uncontrolled hypertension (systolic BP>140 mm Hg or diastolic BP>90 mmHg on repeated measurement despite optimal medical management).
6. Any hemorrhage or bleeding event \geq NCI CTCAE Grade 3 within 4 weeks prior to start of study medication.
7. Persistent proteinuria \geq Grade 3 on repeated measurement
8. Substance abuse, medical, psychological or social conditions that may interfere with the patient's participation in the study or evaluation of the study results.
9. Subjects with an arterial thrombotic or thromboembolic event within 12 months of informed consent.
10. Ascites, pleural effusion, or pericardial fluid requiring drainage in the last 4 weeks
11. Known history of human immunodeficiency virus (HIV) infection or current chronic or active hepatitis B or C infection requiring treatment with antiviral therapy.
12. Clinically significant cardiovascular disease such as unstable angina, uncontrolled or symptomatic arrhythmia, congestive heart failure, any Class 3 or 4 cardiac disease as defined by the New York Heart Association Functional Classification, or history of myocardial infarction within 6 months prior to first dose with study drug
13. Unable to swallow capsules or disease significantly affecting gastrointestinal function and/or inhibiting small intestine absorption such as; malabsorption syndrome, resection of the small bowel, or poorly controlled inflammatory bowel disease affecting the small intestine.
14. Child-Pugh B cirrhosis (or worse) or a history of hepatic encephalopathy
15. History of stroke or intracranial hemorrhage within 6 months prior to enrollment.

16. Any illness or medical conditions that are unstable or could jeopardize the safety of the patient and his/her compliance in the study.
17. Major surgery or a wound that has not fully healed within 4 weeks of enrollment.
18. Patients who need anticancer chemotherapy other than the study drugs during the study or within 4 weeks of study enrollment. Anti-cancer therapy is defined as any agent or combination of agents with clinically proven anti-tumor activity administered by any route with the purpose of affecting the malignancy, either directly or indirectly, including palliative and therapeutic endpoints.
19. Patients who need hormonal therapy during the study or within 2 weeks of first study enrollment.
20. Patients who need radiotherapy to target lesions during study or within 2 weeks of enrollment.
21. Patients who had bone marrow transplant or stem cell rescue.
22. Patients who need investigational drug therapy outside of this trial during or within 4 weeks of first study treatment.

